2.2.1. Clinical Overview

As of September 2021, a total of 32 participants were enrolled from 2 to 10 years old. 14 participants were randomized to 1 mg/kg once weekly (QW) arm and 15 participants were randomized to 2 mg/kg twice weekly (BIW) dosing arm and 3 participants were randomized to 1.5 mg/kg daily (QD). A total of 36 treatment related AEs were reported from 13 out of 32 participants; 3 at low dose, 8 at medium dose and 2 at high dose. The most frequently reported AEs were ISRs such as redness/rash/erythema/pruritis at the injection site. All AEs were mild or moderate in severity and there were no serious adverse events. There were no other clinically significant laboratory abnormalities or physical examination/vital sign changes. Following, administration of study drug, observed serum recifercept concentrations at all three doses were in the range of the predicted exposures in 2 to <10 year old children with achondroplasia using the population PK (PopPK) model.

In the recifercept Phase 1 study (C4181002), healthy participants were administered single (n=30) and multiple (n=24) SC doses of recifercept. In addition, 18 participants received placebo in the study. The dose-range studied in single ascending dose (SAD) part of the study was 0.3 – 20 mg/kg and in the multiple ascending dose (MAD) part was 1 mg/kg and 3 mg/kg twice weekly and 3 and 10 mg/kg once weekly for four weeks. Signs and symptoms of an injection site/infusion site reaction, including erythema, swelling, pain, inflammation, and pruritis, were the most frequently reported adverse events in the SAD and MAD part of

the study. There were no clinically significant changes in laboratory tests, vital signs or ECG. No systemic allergic reactions or serious adverse events occurred during the study.

In the SAD portion of the study, all participants were ADA negative (ADA-) prior to treatment with reciferecept. A confirmed ADA positive (ADA+) response was observed in 8 participants receiving reciferecept and 1 placebo participant at the end of the study (Day 29). In the MAD portion of the study, 2 participants were ADA+ prior to treatment with reciferecept. The majority of the participants who received multiple doses of reciferecept were ADA+ (21/24) and 2 placebo participants during the observation period.

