9.2. Sample Size Determination

Sample size determination is based on the co-primary endpoint of height growth, defined as change from baseline of height at 12 months for participants on drug versus change from baseline of height at 12 months for a reference achondroplasia population. A total of 54 participants randomized to three dose levels in order to obtain 15 participants per dose, assuming a one-sided family-wise error rate of 0.05 with a Bonferroni correction (0.017 after Bonferroni adjustment for 3 comparisons), and inter-participant variability of .15 (estimated from C4181001), there is over 90% power to detect at least one dose providing 50% height growth above reference. No statistical comparison will be made between recifercept doses.

PK Study Cohort:

No formal sample size calculation was performed and 12 participants will be selected empirically to characterize PK, safety and tolerability after single 3 mg/kg dose administration of two formulations.

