9.5. Interim Analyses

Interim analyses may be performed to assess efficacy and safety after approximately 45 participants (up to 15 per dose), complete their study participation through 50% of the study (completion of 6 months treatment). Before any interim analysis is instigated, the details of the objectives, decision criteria, dissemination plan, and method of maintaining the study blind as per Pfizer's SOPs will be documented and approved in a charter. In addition, the analysis details must be documented and approved in an interim analysis SAP or final SAP.

The Bonferroni correction method is used to control the overall familywise error rate of 0.05 for multiple comparisons. The post-baseline estimate will be considered statistically significant at the 1-sided 0.017 level. No statistical comparisons will be performed between treatment arms.

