2. INTRODUCTION

This statistical analysis plan (SAP) provides the detailed methodology for summary and statistical analyses of the data collected in Study C4181005. This document may modify the plans outlined in the protocol; however, any major modifications of the primary endpoint definition or its analysis will also be reflected in a protocol amendment.

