5.2.1. Analyses for Longitudinal Continuous Endpoints

Mixed-effect, repeated measures (MMRM) models will be used. The fixed effects of treatment, visit, treatment-by-visit interaction, age and gender will be included. Visit will be modeled as a categorical covariate. (If the model does not converge then Visit will be modeled as a continuous covariate.) Unstructured covariance matrix will be assumed for the model errors. Compound symmetry covariance matrix will be used if the model with unstructured variance covariance doesn't converge.

When modeling the change from baseline values, the variable for visit will start with the first post-baseline visit. At each visit, estimates of least square mean (LSM) values and the LSM differences between treatment groups will be derived from the model. The corresponding p-values and 95% confidence intervals will also be derived from the model.

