6. ANALYSES AND SUMMARIES

6.1. Primary Endpoint(s)

6.1.1. Increase in height growth above expected in reference population

6.1.1.1. Main Analysis

- Estimand strategy: Hypothetical ([Section 2.1.1](#)).
- Analysis set: FAS ([Section 4](#)).
- Analysis methodology: Change from baseline relative to Merker (2018) will be analyzed using MMRM including data from Months 3, 6, 9, and 12 with gender (and possibly age) as a covariate, subject (and/or time) as a random effect and an unstructured covariance matrix ([Section 5.2.1](#)).
- Intercurrent events and missing data: Data after study drug discontinuation and rescue will be excluded; intermediate missing values will not be imputed.
- The sample size, mean, standard deviation, median, minimum, and maximum at the baseline and postbaseline visits for observed standing height and change from baseline will be presented for each treatment arm.
- The least-squares (LS) means, the 95% confidence interval for the LS means, the difference between the LS means for each pair of treatment groups, and the corresponding 95% confidence interval will be presented for change from baseline in standing height for all postbaseline visits.

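### The SAP plans pairwise dose differences, with intervals and p-values, that the protocol rules out; the two high-dose contrasts are also at risk of confounding by enrolment period

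*SAP*

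**What the plan says.** **Protocol.** Section 9.2 says "No statistical comparison will be made between recifercept doses", and the synopsis repeats this. Section 9.5, on the interim analysis, says "No statistical comparisons will be performed between treatment arms". The only hypothesis in 9.1 sets growth on recifercept against growth in the external reference population. The one-sided 0.017 level in 9.2 and 9.5 is 0.05 split over the three doses.

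**SAP.** Section 6.1.1.1 plans that "the difference between the LS means for each pair of treatment groups, and the corresponding 95% confidence interval will be presented", for change in standing height at all post-baseline visits. Section 6.1.1.2 repeats the analysis in the per-protocol set. Section 6.2.1.1 (arm span to height difference) has the same sentence, still worded for standing height. Section 7.2 has it for the interim, using Months 3 and 6. The general model text in 5.2.1, which these sections cite, says that at each visit "estimates of least square mean (LSM) values and the LSM differences between treatment groups will be derived from the model", and then "The corresponding p-values and 95% confidence intervals will also be derived from the model". SAP 5.1 repeats the protocol's Bonferroni text but not the sentence that bars comparisons between arms.

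**Enrolment.** Protocol 4.1 describes enrolment staggered from older to younger children and from lower to higher dose. Section 2.2.1 gives the September 2021 counts: 14 low, 15 medium, 3 high. The plan is 18 per dose.

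**The concern.** A statistician following the SAP will produce a table that the protocol says will not exist. SAP section 2 allows the SAP to depart from the protocol, with the proviso that "any major modifications of the primary endpoint definition or its analysis will also be reflected in a protocol amendment". The current protocol contains no such change; it still bars the comparisons.

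The output would also be easy to over-read. This is a dose-finding trial, and three differences with 95% intervals and p-values look like confirmatory dose comparisons. They have no multiplicity control. For the two contrasts that involve the high dose, most of the children being compared entered at different times.

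**Working it through.** **1. The plan's own figure.** Inputs from Protocol 9.2: 15 evaluable per dose, 50% growth above reference, variability 0.15, one-sided 0.05/3 = 0.0167 (printed as 0.017). I take 0.15 as the SD of the growth ratio, which is an assumption about scale. For a one-sample t test of 1.5 against 1.0, the noncentrality is (0.5/0.15) × √15 = 12.9 and power is about 1.00. The stated power of over 90% is reproduced. It concerns each dose against the reference and does not depend on the pairwise output.

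**2. Multiplicity of the pairwise output.** Three doses give three differences per visit. With 15 per dose there are 42 residual degrees of freedom, and the 5% two-sided critical value is t = 2.018. If all doses are equal, the chance that at least one unadjusted interval excludes zero is P(Q > √2 × 2.018) = P(Q > 2.85), where Q is the studentized range for 3 groups and 42 df. The result is 0.120. Treating the contrasts as independent would give 1 − 0.95³ = 0.143, but any one of the three is determined by the other two, so 12% is the right figure.

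Over Months 3, 6, 9 and 12 there are 3 × 4 = 12 intervals. Simulation (20,000 trials, 15 per dose) gives the chance that at least one excludes zero:

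| Assumed between-visit correlation | At least one of 12 excludes zero |
|---|---|
| 0.9 | 21% |
| 0.8 | 25% |
| 0.5 | 34% |
| 0.3 | 38% |

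The documents do not give this correlation.

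**3. Concurrency.** September 2021 counts against the planned 18 per dose:

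| Dose | Randomised | Share of plan | Still to enter |
|---|---|---|---|
| Low | 14 | 78% | 4 |
| Medium | 15 | 83% | 3 |
| High | 3 | 17% | 15 |

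Low and medium together are 29/36 = 81%. Low and medium filled side by side, while most of the high-dose group was still to enter.

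**4. What the model adjusts for.** SAP 5.2.1 lists treatment, visit, their interaction, age and gender. Section 6.1.1.1 makes age optional. No version has a term for enrolment block or calendar time.

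**5. Size of the risk (illustration only).** Suppose the growth ratio drifts by D between the early and late periods. The bias in high minus low is D × (15/18 − 4/18) = 0.61D, and in medium minus low D × (3/18 − 4/18) = −0.06D. For an assumed D of 0.05 to 0.15, high minus low is biased by 0.03 to 0.09, while medium minus low moves by less than 0.01. With SD 0.15, the half-width of a pairwise 95% interval at 15 per dose is 2.018 × 0.15 × √(2/15) = 0.11. At 18 per dose, the two-sided 5% error for high versus low would rise to about 9% at D = 0.05 and 44% at D = 0.15. The documents give no estimate of D.

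**The case against.** Several points on the other side are sound.

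- **No decision rests on these differences.** SAP 5.1 attaches its decision rule only to dose versus reference. The 12% is therefore a chance of a misleading interval, not an error rate of a declared test. A reader might infer that the contrasts will select the dose, but no document says so. Protocol 6.6.1 ties dose adjustment after the interim to overall benefit and risk, and SAP 7.1 mentions only internal business decisions.
- **The p-values appear only in the general text of 5.2.1**, where the wording can refer to the means, the differences or both. Sections 6.1.1.1, 6.2.1.1 and 7.2 mention intervals alone. This makes the p-values less certain but leaves the intervals in place.
- **Age is partly handled.** The primary endpoint is divided by expected growth for age and gender, and age is a listed model term in 5.2.1 and Appendix 1. SAP 5.2 also presents data by block. None of this adjusts the contrasts for block or calendar time. The pairwise output is described for change in standing height, which reads as the unstandardised measure.
- **Concurrency is known only from a snapshot during enrolment**, set against planned totals. A reader might also infer that children in the early blocks had no access to the high dose. The documents do not establish this: the schema is not shown, and the Block B to C review already counts three older children on the high dose.

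The SAP's latitude to modify the protocol does not resolve the conflict. Even if the change were called minor, the two current texts cannot both be followed. The SAP is also not consistent with itself: its Appendix 4 code has no dose-by-month term and requests no differences, so it would not produce the per-visit contrasts that 6.1.1.1 describes.

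**Conclusion.** The conflict is plain on the text and should be resolved before database lock. The protocol bars statistical comparison between doses. The SAP presents all three pairwise differences at every visit, interim included, with unadjusted 95% intervals and, through 5.2.1, p-values. The multiplicity is about 12% per visit for three equal doses with 15 children each.

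The confounding argument applies to high versus low and high versus medium only. Extending it to all pairwise contrasts is not supported, because low and medium enrolled together. It is a risk and not a demonstrated bias: the drift figures rest on assumed values, and neither the final age mix nor the final timing by dose is given. It would also be wrong to infer that the primary analysis is compromised. The test of each dose against the reference, its 0.017 level and its power do not use these contrasts.

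**What to change.** Delete the pairwise LS-mean differences, with their intervals and p-values, from SAP 5.2.1, 6.1.1.1, 6.2.1.1 and 7.2. Keep what is needed for each dose against the reference. This costs SAP wording only; sample size and power do not change, and the Appendix 4 code already requests no differences.

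If the sponsor wants the contrasts, amend Protocol 9.2, 9.5 and the synopsis to allow them. Label them descriptive, give no p-values, and state beside the two high-dose contrasts that they are largely non-concurrent. A sensitivity analysis limited to children enrolled while the high dose was open to them may be added. It would lose precision, since many low- and medium-dose children could drop out of the comparison. Adding a block term to the model is not a cheap substitute: blocks were built from age and dose, so the term would be partly aliased with dose.

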6.1.1.2. Sensitivity/Supplementary Analyses

The main analysis will be repeated by using the per-protocol analysis set (PPAS) as defined in [Section 6.1.1.1](#). It will use the same methodology and summary as the main analysis.

6.1.2. PK Cohort

Blood samples for PK analysis of Intact and total recifercept will be taken according to the Schedule of Activities given in the protocol.

The following PK parameters will be calculated for intact and total recifercept from the concentration-time values using standard non-compartmental methods:

Table 2 Non-compartmental PK Parameters

Parameter	Analysis Scale	Recifercept
C_{\max}	ln	D
T_{\max}	U	D

$t_{1/2}^*$	U	D
AUC_{inf}^*	ln	D
AUC_{168}^*	ln	D
AUC_{360}^*	ln	D

Key: A=analyzed using statistical model, D=displayed with descriptive statistics,
ln=natural-log transformed, U=raw (untransformed), *=if data permits.

To assess the pharmacokinetics of intact and total recifercept, the PKP parameters detailed above will be listed and summarized for subjects in the PK analysis set (as defined in [Section 4](#)). Missing values will be handled as detailed in [Section 5.3.1](#). Each PK parameter for intact and total recifercept will be summarized by dose. Each summary will include the set of summary statistics as specified in [Table 3](#).

Table 3 PK Parameters to be Summarized Descriptively

Parameter	Summary Statistics
AUC_{360} , AUC_{inf} , AUC_{168} , C_{max}	N, arithmetic mean, median, cv%, standard deviation, minimum, maximum, geometric mean and geometric cv%.
T_{max}	N, median, minimum, maximum.
$t_{1/2}$	N, arithmetic mean, median, cv%, standard deviation, minimum, maximum.

There will be a summary table each for Intact and Total Recifercept presenting all PK parameters. Each summary table will be grouped by dose.

To assess the relationship between the PK parameters and dose, dose normalized AUC_{tau} and C_{max} will be plotted against dose (using a logarithmic scale), and will include individual subject values and the geometric means for each dose separately. Geometric means will have a different symbol than the individual values. The values will be dose normalized (to a 1 mg/kg dose) by dividing the individual values and raw geometric means by dose. A footnote will be added to the plots to indicate that geometric means are presented.

Supporting data from the estimation of $t_{1/2}$ and AUC_{inf} will be listed where applicable: terminal phase rate constant (k_{el}); goodness of fit statistic from the log-linear regression (r^2); the percent of AUC_{inf} based on extrapolation ($AUC_{extrap\%}$); and the first, last, and number of time points used in the estimation of k_{el} . These data may be included in the clinical study report.

Presentations for intact and total recifercept concentrations will include:

A listing of all concentrations sorted by subject ID, dose, and nominal time post-dose. The concentration listing will also include the actual times. Deviations from the nominal time will be given in a separate listing.

A summary of concentrations by dose, cohort, and nominal time post-dose, where the set of statistics will include n, mean, median, standard deviation, coefficient of variation (cv), minimum, maximum and the number of concentrations above the lower limit of quantification.

Median concentrations time plots (on both linear and semi-log scales) against nominal time post-dose by dose and cohort (all doses on the same plot per scale, based on the summary of concentrations by dose, cohort and time post-dose).

Mean concentrations time plots (on both linear and semi-log scales) against nominal time post-dose by dose and cohort (all doses on the same plot per scale, based on the summary of concentrations by dose, cohort and time post-dose).

Individual concentration time plots by dose and cohort (on both linear and semi-log scale) against actual time post-dose will be produced.

The length of time used for the x-axes of these plots will be decided on review of the data, and will depend on how long reciferecept concentration is quantifiable in the matrix.

For summary statistics, median and mean plots by sampling time, the nominal PK sampling time will be used, for individual subject plots by time, the actual PK sampling time will be used.

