The serum PK parameters for recifercept will be summarized descriptively by formulation. Serum concentrations will be listed and summarized descriptively by formulation and nominal PK sampling time. Individual participant summary profiles (mean and median plots) of the serum-concentration time data will be plotted by formulation and PK sampling time. For summary statistics and summary plots, the nominal PK sampling time will be used. For individual participant plots, the actual PK sampling time will be used, whilst the pre-dose will be set to zero. Summary plots will be presented on both linear-linear and log-linear scales.

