4. ANALYSIS SETS (POPULATIONS FOR ANALYSIS)

Data for all participants will be assessed to determine if participants meet the criteria for inclusion in each analysis population prior to unblinding and releasing the database and classifications will be documented per standard operating procedures.

Population	Description
Full Analysis Set (FAS)/Safety	All participants receiving at least one dose of reciferecept. Participants will be analyzed according to the dose they actually received.
Per-Protocol Analysis Set (PPAS)	All participants receiving at least one dose of reciferecept and have complete data at baseline through month 12 and without protocol deviations that were thought to impact the efficacy evaluation during the treatment period. Participants will be analyzed according to the randomized intervention.
PK Concentration set	All participants who received at least one dose of reciferecept and have at least one evaluable concentration.
PK Study Cohort	All participants who received a dose of the reciferecept Phase 2 formulation and a dose of the Phase 3 formulation with at least one evaluable concentration result.

Population	Description
PK Study Cohort Parameter (PKCP)	All participants in the PK cohort who have at least one PK parameter of interest.

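### SAP 6.1.2 groups the PK-cohort outputs by dose, not by formulation as the protocol requires; both formulations share one dose, so the tables would mix them

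*SAP*

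**What the plan says.** Protocol Section 3 makes the PK of the two formulations the primary objective of the PK cohort. Protocol 4.1 and its Table 1 describe a two-sequence crossover with 6 children per sequence, in which each child receives process 1c and process 2, both at 3 mg/kg. Protocol 9.4.2 says the serum parameters "will be summarized descriptively by formulation", and also lists, summarises and plots the concentrations by formulation. Protocol 9.4.7 gives evaluation of the two formulations as the purpose of the non-compartmental analysis.

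SAP 6.1.2 sets different groupings:

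- Parameters: "Each PK parameter for intact and total recifercept will be summarized by dose".
- Tables: "Each summary table will be grouped by dose".
- Concentration listing: "A listing of all concentrations sorted by subject ID, dose, and nominal time post-dose".
- Concentration summary: "A summary of concentrations by dose, cohort, and nominal time post-dose". The mean, median and individual plots are by dose and cohort.
- A dose-relationship plot of dose-normalised AUCtau and Cmax: "To assess the relationship between the PK parameters and dose".
- Population: parameters are "listed and summarized for subjects in the PK analysis set".

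In the SAP text available, formulation appears only in Section 4. There the PK Study Cohort set requires a dose of the Phase 2 formulation "and a dose of the Phase 3 formulation with at least one evaluable concentration result".

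**The concern.** Grouping by dose separates treatments only if they differ in dose. Here they do not, and adding cohort does not help because both formulations sit in the same cohort. The protocol's grouping answers the cohort's question; the SAP's grouping cannot.

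The output at stake is the primary one for this cohort, on which the two manufacturing processes are to be described before Phase 3. Data collection is not affected. The risk is that shells and programs are built from SAP 6.1.2 and the primary PK tables come out pooled.

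Two other items in the section suggest text written for a multi-dose study. The dose-relationship plot would have one point on its dose axis, and AUCtau is not among the cohort's parameters in SAP 3.1.1 or in Table 2 of SAP 6.1.2. The analysis set that the section cites is not defined under that name in SAP Section 4.

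**Working it through.** The plan has no figure to reproduce: protocol 9.2 says the 12 participants were chosen empirically. The check is a count of groups, followed by an illustration of what pooling hides.

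**Inputs from the documents.** 12 children, 6 per sequence, 2 periods, 3 mg/kg in both periods (protocol 4.1); 2 analytes, intact and total (SAP 6.1.2).

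**Count of groups.** Profiles per analyte = 12 × 2 = 24; over both analytes, 24 × 2 = 48. These are maxima, reached if every child completes both periods.

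| Grouping | Groups | Profiles per group, per analyte |
|---|---|---|
| Dose (SAP parameter tables) | 1 | up to 24 |
| Dose and cohort (SAP concentration summaries and plots) | 1 | up to 24 |
| Formulation (protocol 9.4.2) | 2 | up to 12 each |

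**Listing and nominal times.** The time headings that can be read in the PK-cohort schedules (protocol 1.3) give 11 times common to both periods: 0, 2, 6, 12, 24, 48, 72, 120, 168, 264 and 408 h. At each of these a child has two records with the same subject, dose and nominal time, one per formulation. The SAP's sort keys do not tell them apart.

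**Missing-data rules.** SAP 5.3.1 withholds summary statistics at a time point when more than half the data are missing. In the pooled group, one formulation could be wholly missing at a time point: 12/24 = 50%, which is not more than half, so the statistics would still be shown.

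**What the pooled column would show (illustration).** The documents give neither a formulation ratio nor a CV, so both are assumed. Let R be the true process 2 to process 1c ratio of geometric means, with equal numbers and the same geometric CV in each formulation.

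- Pooled geometric mean relative to process 1c = √R. At R = 0.80, √0.80 = 0.89; at R = 1.25, √1.25 = 1.12.
- Pooled geometric CV = √(exp(ln(1 + CV²) + (ln R)²/4) − 1). For R = 0.80 or 1.25, (ln R)²/4 = 0.0124.

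| Assumed CV in each formulation | ln(1 + CV²) | Pooled CV at R = 0.80 or 1.25 |
|---|---|---|
| 30% | 0.0862 | 32.2% |
| 40% | 0.1484 | 41.8% |
| 50% | 0.2231 | 51.5% |

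Larger differences inflate the spread more. With CV 30%, the pooled CV is 36.8% at R = 1.5 and 47.9% at R = 2.0. Even then, R cannot be recovered from the table, because a wide spread could equally come from variation between children.

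**The case against.** The strongest case is that the protocol already settles the matter. Section 9.4.2 fixes grouping by formulation, and SAP Section 2 says that major modifications to the primary endpoint's analysis will also appear in a protocol amendment. None drops formulation. A pooled output therefore needs a programmer to follow SAP 6.1.2 and overlook the protocol. That is fair: this is a conditional risk rather than a decision to pool. But the SAP is the document that gives the detailed methods, its cohort section contradicts the protocol, and its version history records no decision on grouping.

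A second argument is that dose could mean an administration, since the protocol speaks of one dose of each formulation. The same SAP section normalises values to 1 mg/kg by dividing by dose, so there the word means an amount.

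Smaller points stand in part:

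- The SAP gives sort keys for the listing, not its full set of columns, so a formulation column is not excluded. It is simply not specified.
- Protocol 4.3 places a change of the cohort dose before the cohort starts; the synopsis and Section 4.1 give no timing. Either way the change is to the cohort's dose, so dose would still not identify formulation.
- The dose-and-cohort concentration displays may be meant to serve the main regimens too. The correction should therefore apply to PK-cohort outputs and leave any main-study displays in place.

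**Conclusion.** The concern holds. As written, SAP 6.1.2 contradicts protocol 9.4.2 on the cohort's primary PK output. Followed literally, it gives one mixed column of up to 24 profiles per analyte instead of two of up to 12. That result rests only on the documented design: both formulations at one common dose, in one cohort. The pooled means and CVs are illustrations under assumed values of R and CV, and the conclusion does not depend on them.

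The protocol wording is right, no data are lost and outputs could be rerun. It is a SAP error that should be corrected before programming, not a flaw in the design.

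**What to change.** In SAP 6.1.2, for PK-cohort outputs:

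1. Replace grouping by dose with grouping by formulation in the parameter tables, concentration summaries, and mean and median plots.
2. Add formulation and period as identifiers in the listings and individual plots.
3. Remove the dose-normalised AUCtau and Cmax plot from this section. If it is meant for the main-study regimens, move it there and say so. Keep any by-dose concentration displays intended for those regimens, labelled as such.
4. Name the Section 4 set intended in place of the undefined one, for example PKCP for parameters.

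The cost is SAP wording and table shells. No extra samples, participants or protocol change is needed.

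An optional addition, which corrects no error: report the within-child process 2 to process 1c geometric mean ratio with a 90% confidence interval from a standard crossover model, labelled as estimation only. The plan is descriptive and can remain so.
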